Version #	Version Date	Significant Changes from Previous Version
01	02/03/2016	Original Protocol Version
02	04/25/2016	Added additional justification for sample size
03	06/28/2016	Change randomization for the first 3 subjects to naloxone
04	01/05/2017	Add 8mg dose of naloxone; change randomization for the first 8 subjects to naloxone
05	01/31/2019	Update study location

Table of Contents

List of Abbreviations	.6
1.0 Study Contact Information	.7
2.0 Introduction / Background and Rationale	.8

Study Summary

Title	Intra-nasal Naloxone for treatment of impaired awareness of hypoglycemia
Short Title	Intra-nasal Naloxone for impaired awareness of hypoglycemia
IRB Number	1603M84961
Study Sponsor	[name]
Phase	1
Principal Investigator	[name]
Study Design	Single center, single-blind, randomized, cross-over
Study Duration	24 months
Study Center(s)	Clinical Research Unit (CRU)
Objectives	Primary Objective: To evaluate intra-nasal Naloxone as a therapy for prevention and treatment of impaired awareness of hypoglycemia.
	Secondary Objective: Characterize naloxone pharmacokinetics following multiple administrations.
Number of Subjects	18
Main Inclusion Criteria	Males and females between the ages of 18-65 years
Study Product, Dose, Route, Regimen	Narcan (naloxone hydrochloride) intranasal spray, 4 mg/nostril repeated 4 times within 8 hours alternating nostrils.
Duration of Administration	4 doses of 4 mg or 2 doses of 8 mg administered over 1 day.
Endpoints	Primary endpoint will be the within person difference in peak epinephrine secretion during the morning episodes of hypoglycemia on days one and two; we will compare this difference between the two treatment conditions.
	Secondary endpoint will be naloxone pharmacokinetics including maximum concentration (Cmax), time to maximum concentration (Tmax) and area under the curve (AUC).
Statistical Methods	We will fit a general linear mixed model with fixed effects for treatment (naloxone vs. placebo), treatment order (naloxone first vs. placebo first), and period (Part 1 vs. Part 2) and a random effect for participant. We will also consider adjustment for important baseline characteristics, such as age and sex. Diagnostics will be examined to assess model assumptions.

List of Abbreviations

AE	Adverse Event	
CFR	Code of Federal Regulations	
CRF	Case Report Form	
DSMB	Data and Safety Monitoring Board	
DSMP	Data and Safety Monitoring Plan	
FDA	Food and Drug Administration	
GCP	Good Clinical Practice	
HIPAAHealth Insurance Portability and Accountability Act of 1996		
ICH	International Conference on Harmonization	
IDS	Investigational Drug Services	
IRB	Institutional Review Board	
PHI	Protected Health Information	
SAE	Serious Adverse Event	

2.0 Introduction / Background and Rationale

Iatrogenic hypoglycemia is a common and feared complication of insulin therapy. Recurrent exposure to iatrogenic hypoglycemia in patients with insulin treated diabetes can lead to development of impaired awareness of hypoglycemia (IAH) (1), a condition that is estimated to occur in 20% of patients with type 1 diabetes (T1D) (2). Fear of hypoglycemia can limit the ability of patients with diabetes to achieve the glycemic control shown to prevent complications of diabetes. Strict avoidance of hypoglycemia has been shown to partially restore awareness of hypoglycemia; however it is very difficult to achieve and maintain over the long term (3-5). Consequently, there has been great interest in developing therapies that will prevent and/or reverse IAH in diabetes.

One potential therapy to prevent or reverse IAH in diabetes may be opioid receptor antagonists. Endogenous opiates have been shown to modulate hormonal responses during hypoglycemia and may play a role in the development of IAH (6). Intravenous (IV) administration of naloxone, an opioid receptor antagonist, during hypoglycemia has been shown to augment the counterregulatory response to hypoglycemia in dogs (7) and humans (8). When infused during antecedent hypoglycemia, IV naloxone has been shown to prevent development of defective counterregulatory hormone response to subsequent hypoglycemia in healthy humans (9) and in patients with T1D (10). However, IV dosing of Naloxone is not feasible for chronic outpatient therapy. The usual alternative of oral dosing is hindered by large first pass effects, low oral bioavailability, and high variability. Intra-nasal (IN) route of administration is a novel approach to provide adequate systemic exposure in easy to use delivery route. IN naloxone is currently being used for acute management of opioid overuse.

The long-term goal of this project is to test the hypothesis that IN naloxone therapy in subjects with T1D and IAH will improve counter regulatory hormone responses during hypoglycemia and increase recognition of hypoglycemia symptoms. The purpose of this project is to evaluate IN naloxone as a therapy for the prevention and treatment of IAH. IAH can be reproduced experimentally by inducing recurrent hypoglycemia in healthy subjects (11), providing a robust investigational model for studying mechanism and treatments for IAH. In this study we will test the hypothesis that IN naloxone therapy will prevent the development of IAH in healthy subjects who are exposed to experimental hypoglycemia.

Rationale for route of administration, dose, and regimen: Intranasal delivery was selected in order to non-invasively produce similar naloxone concentrations to those attained from the IV dosing used in previous studies which demonstrated the beneficial effects of naloxone (9,10). Two, 4 mg doses, one to each nostril, administered 1 hr apart are expected to produce similar naloxone concentrations as a 0.4 mg/kg/mL dose administered over 90 minutes which was the dose used for the IV study (9). The half-life is reported to be 2.1 hours (Narcan package label) suggesting the drug will remain at elevated levels for ~ 4 hours (2 half-lives) after the second dose. A third 4 mg dose will be administered ~4 hrs after the second to remain levels similar to intravenous dosing. When a single 8 mg dose was administered to healthy volunteers, adverse events included increased blood pressure, musculoskeletal pain, headache, nasal dryness, nasal edema, nasal congestion, and nasal inflammation. These symptoms will be monitored throughout the study.

3.0 Investigational Agent(s)

3.1 Description / Indications

Narcan[®] (naloxone hydrochloride) intranasal spray (4 mg in 0.1 mL) will be used for this study. Narcan[®] intransal spray, manufactured by ADAPT Pharma is approved by the FDA for the complete or partial reversal of opioid depression, including respiratory depression, induced by natural and synthetic opioids. The placebo will consist of a saline intranasal spray (0.09% sodium chloride).

3.2 Drug Accountability

3.2.1 Drug Receipt

The Narcan[®] and placebo intranasal sprays will be shipped from different supplier/ distributer directly to Fairview Investigational Drug Services. For the drug product, the same manufacturer and lot will be used for the entire study.

3.2.2 Packaging

The subjects will receive four 4 mg doses or two 8 mg doses of IN naloxone or placebo which will be dispensed by Fairview Investigational Drug Services, prepared by the Investigators and given to the subject on site. No packaging will be necessary, as no study drug will leave the site.

3.2.3 Storage

Naloxone hydrochloride and placebo intranasal solutions can be stored at room temperature 15C to 25° C.

3.2.4 Return or Destruction of Study Drug

Unused drug will be returned to IDS where it will be destroyed under standard operating procedures.

4.0 Study Objectives

4.1 **Primary Objective**

Primary endpoint will be the within person difference in peak epinephrine secretion during the morning episodes of hypoglycemia on days one and two; we will compare this difference between under the two treatment conditions (parts 1 and 2). Epinephrine secretion during hypoglycemia is assessed by collecting blood samples for measurement of epinephrine concentrations at baseline and every 15 minutes during the period of hypoglycemia (starting at point where blood glucose is first < 55 mg/dl) in the clamp studies done in the mornings of days 1 and 2 of both parts 1 and 2.

4.2 Secondary Objective

Characterize naloxone pharmacokinetics following multiple intranasal administrations.

5.0 Study Design

5.1 Overview of Study Design

This is a single center, single-blind randomized cross over design trial that will compare the impact of intra-nasal naloxone vs. intra-nasal placebo administration during experimental hypoglycemia on day one vs. day two. We intend to enroll 18 individuals to obtain the complete data sets from 15 participants. Initially up to 8 of these subjects will receive intra-nasal naloxone first prior to placebo in order to evaluate tolerability and to ensure that the desired drug concentrations are achieved. Double-blinding is not possible because we will not be able to replicate for the placebo (placebo) the same delivery device as is being provided by the manufacturer for the naloxone; the manufacturer is unable to provide placebo-charged devices for us to use as placebo. Our own labeling will be put over both naloxone and placebo devices in order to obscure any device labeling that would break the blind for the participant. Expected duration of subject participation is 10-12 weeks. This study will consist of two 2-day intervention visits separated by approximately 8 weeks.

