5.4.1 Sample Size

We plan to enroll 18 subjects.

We propose a two-period two-treatment cross-over study, where each participant gets intra-nasal naloxone and intra-nasal placebo, in randomized order. Primary endpoint will be the within person difference in peak epinephrine secretion during the morning episodes of hypoglycemia on days one and two; we will compare this difference between under the two treatment conditions. Thus each participant will have two observations: one epinephrine response from their naloxone experiment and one epinephrine response from their placebo experiment. We expect to recruit 18 individuals in order to complete 15 studies. Additional participants will be recruited if needed to have 15 completed studies. If naloxone prevents IAH, then the epinephrine response during the third hypoglycemic clamp after naloxone infusion will still be high, while the epinephrine response during the third hypoglycemic camp after placebo infusion will be large and positive. If naloxone does not prevent IAH, then this within-person difference will be close to zero.

In a previous study between healthy controls and subjects with T1D and impaired awareness of hypoglycemia, participants underwent a hyperinsulinemic hypoglycemic clamp (the same clamp procedure as proposed here) and the epinephrine response (the difference in peak epinephrine between euglycemia and hypoglycemia) was 121 ± 168 pg/ml in the subjects with T1D vs. 278 ± 134 pg/ml

in controls. We have powered this study to achieve a similar magnitude of difference between naloxone and placebo (a paired comparison) as was seen previously between controls and diabetics (a two-sample comparison). Assuming 15 completers, a one-sided type I error of 5%, and a power of 85%, a paired difference between naloxone epinephrine response and placebo epinephrine response of at least 157 pg/ml is statistically detectable if the between-person standard deviation of the paired naloxone vs. placebo difference is *no more than* **216** pg/ml.

This standard deviation of the paired difference is a function of the standard deviation of the epinephrine response and the within-person correlation between the two epinephrine responses (one after naloxone, one after placebo). As can be seen from the Table below, we are conservatively powered, as our preliminary data suggest that our observed standard deviation will be smaller than 216 pg/ml.

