Table. Estimated standard deviation (SD) of the paired difference between naloxone epinephrine response and placebo epinephrine response when the within-person correlation is ρ

	$\rho = 0.2$	ρ = 0.4	ρ = 0.6	$\rho = 0.8$
SD in epi response = 135	171	148	121	85
SD in epi response = 170	215	186	152	108

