6.2 Randomization Scheme

The investigational pharmacy at the University of Minnesota will be responsible for implementing the randomization order in which participants are given naloxone or placebo, prepared by the study statistician.

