6.7 Study Protocol Compliance / Treatment Adherence

Safety and tolerability will be evaluated in all subjects who receive study drug whether or not they complete the study. Subjects are required to stay at CRU research facility for 3 hours after the last dose of study drug administration. If they do not complete the study; a new subject will be recruited to ensure a final sample size of 15 completers.

6.8 **Protocol Amendments after Study Initiation**

Should changes in the study plan or protocol become necessary in the course of the clinical trial, those specific changes will be discussed and agreed upon by the Investigators, and appropriate IRB approval obtained before the changes are implemented. All changes must be documented as protocol amendments.

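### The 85% power and 216 pg/ml SD ceiling in 5.4.1 assume a paired t-test with randomized order, but up to 8 subjects are fixed to naloxone first and the 7.2 model makes power depend on the sequence split

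*Combined protocol and SAP*

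**What the plan says.** - **Order of treatment.** Section 5.4.1 describes a two-period crossover "where each participant gets intra-nasal naloxone and intra-nasal placebo, in randomized order". Section 5.1 says "Initially up to 8 of these subjects will receive intra-nasal naloxone first prior to placebo in order to evaluate tolerability". Enrolment is 18, with 15 complete data sets wanted.
- **Power.** Section 5.4.1 takes its difference from an earlier clamp study, with epinephrine responses of "121 ± 168 pg/ml in the subjects with T1D vs. 278 ± 134 pg/ml" in controls, hence 278 − 121 = 157 pg/ml. Its other inputs read "Assuming 15 completers, a one-sided type I error of 5%, and a power of 85" (per cent), with a paired-difference SD of at most 216 pg/ml. It concludes that "we are conservatively powered, as our preliminary data suggest that our observed standard deviation will be smaller than 216 pg/ml", and tabulates SDs for a response SD of 135 or 170 pg/ml and four correlations.
- **Analysis.** Section 7.2 fits a mixed model with treatment, treatment order and period as fixed effects and participant as a random effect.
- **Allocation.** Section 6.2 says only that the pharmacy "will be responsible for implementing the randomization order in which participants are given naloxone or placebo, prepared by the study statistician". It gives no ratio, block size or rebalancing rule. Section 6.7 says that for a non-completer "a new subject will be recruited to ensure a final sample size of 15 completers", without naming that person's sequence.
- **History.** The version table lists added sample-size justification at version 02 and the naloxone assignment of the first 8 at version 04. It lists no later change to the sample size.

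**The concern.** For up to 8 of 18 subjects the 5.4.1 description of the order is untrue. This affects the power because the planned model separates treatment from period. It can do that only by comparing the two sequences, so the smaller sequence limits precision. A paired t-test ignores sequence, so its power does not depend on the split.

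The stated power and SD ceiling are the only justification given for 15 completers. If the lead-in leaves few placebo-first completers, that justification no longer describes the analysis that will be run. The claim to be conservatively powered would then fail for some of the plan's own planning SDs.

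**Working it through.** **Inputs.** From 5.4.1: difference 157, SD of the paired difference 216, 15 completers, one-sided 5%. From 5.1: up to 8 of 18 fixed to naloxone first. From 7.2: order and period terms. The final split is not stated, so a range is shown.

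**Step 1: reproduce the plan's figure.** Paired t-test, SE = 216/√15 = 55.77, noncentrality 157/55.77 = 2.815, 14 df. Power is 84.9%, and the exact SD for 85% is 215.5. The stated 216 is reproduced. Other versions do not fit: a two-sided t-test gives 74.5%, and a normal approximation gives 87.9% with a ceiling of 226.8.

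**Step 2: the 7.2 model.** Let D be the Part 1 minus Part 2 response. Its mean is (period + treatment) in the naloxone-first sequence and (period − treatment) in the other. The treatment estimate is half the difference between the two sequence means of D, so

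SE = (SD/2)·√(1/n1 + 1/n2), with 15 − 2 = 13 df.

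At 11:4, SE = 108·√(1/11 + 1/4) = 63.06, against 55.77 for the paired test. The variance ratio is 225/(4·11·4) = 1.28. A mixed model with these terms, fitted to simulated 11:4 data, gave the same SE as the two-sample form of this estimator.

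| Split of 15 | Power at SD 216 | SD giving 85% |
|---|---|---|
| 8:7 | 84.5% | 214 |
| 9:6 | 83.3% | 210 |
| 10:5 | 80.7% | 202 |
| 11:4 | 76.2% | 190 |
| 12:3 | 68.7% | 172 |
| 13:2 | 56.7% | 146 |

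**Step 3: which splits are plausible.** Assume that all 8 lead-in places are used, the other 10 are allocated about 1:1, and 3 of 18 are lost at random.

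- *Exactly 5 of 10 placebo-first (13:5 enrolled).* Completers split 10:5 with probability 35%, 11:4 48%, 12:3 16% and 13:2 1%. Expected power is 0.350·80.7 + 0.478·76.2 + 0.159·68.7 + 0.012·56.7 = 76.3%.
- *Simple randomization of the 10.* Expected power is 73.8%.
- *11:4 or more uneven.* Probability 65% (5:5) or 59% (simple).
- *No lead-in, same loss assumption.* 84.2% with 9:9, 82.1% with simple randomization. Eight lead-in subjects therefore cost about 8 points. Three would cost about 1 point (81.2% against 82.1%, simple).

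**Step 4: the plan's own SD table.**

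| Cell | 8:7 | 11:4 | 12:3 |
|---|---|---|---|
| 215 (SD 170, ρ 0.2) | 84.7% | 76.5% | 69.1% |
| 186 (SD 170, ρ 0.4) | 92.5% | 86.2% | 79.7% |
| 171 (SD 135, ρ 0.2) | 95.6% | 90.8% | 85.2% |

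All other cells have smaller SDs and keep more than 85% at these splits. The short cells lie in the row "SD in epi response = 170", which matches the T1D group (SD 168). The SD 135 row, which matches the healthy controls (SD 134), holds at 11:4 and 12:3. At 171, expected power with 8 lead-in subjects is 88% to 91%.

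**The case against.** **The imbalance is assumed.** Section 5.1 says up to 8, and the allocation list is not in the documents. A list weighted to placebo-first fits the text equally well. With 7, 8 or 9 of the remaining 10 placebo-first and 3 of 18 lost at random, expected power at SD 216 is 82.5%, 83.8% or 84.2%. This stands: 11:4 is an illustration, and what the documents establish is that the split is unspecified. It also means that the stated power cannot be checked against the planned model.

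**The effect is confined to high SDs.** The plan treats 216 as a maximum, and at 11:4 seven of the eight table cells keep at least 85%. The exception, 215, is already marginally short at 8:7. This also stands and limits the importance of the point. However, the trial enrols normal volunteers whose response is to be blunted experimentally, and the documents do not say which row then applies.

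**More subjects may complete.** If all 18 completed at 13:5, power at SD 216 would be 84.1%. That is correct, but the plan's claim is made for 15.

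**The planning SD may not be that of the endpoint.** It comes from a euglycemia-to-hypoglycemia response, whereas the endpoint is a day 1 to day 2 difference (5.3.1) or the third-clamp peak (7.2). This is a fair caution about precision. It does not change how the ceiling depends on the split.

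**The lead-in is disclosed and the period term is useful.** Both are true, and neither is criticised. With an uneven split, dropping the period term would let a period effect bias the treatment estimate.

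**Conclusion.** The concern holds. The order wording in 5.4.1 contradicts 5.1, and the 216 pg/ml ceiling belongs to a paired t-test that is not the planned analysis. Under the 7.2 model the stated power is essentially right near balance (84.5% at 8:7) and overstated otherwise, by about 9 points at 11:4 and 16 at 12:3 when the SD is 216. The expected power of 74% to 76% rests on three assumptions: all 8 lead-in places used, about 1:1 allocation afterwards, and random loss of 3 of 18. Splits of 12:3 or worse have probability 17% (5:5) to 33% (simple) under those assumptions.

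The trial is not invalidated. At the SDs seen in healthy controls, power stays at or above 85% down to 12:3. The statement should be corrected because no text secures the near-balanced split it needs.

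**What to change.** 1. In 5.4.1, replace the statement that every participant's order is randomized. Say that up to the first 8 form a non-randomized naloxone-first lead-in and that only the rest are randomized.
2. In 5.4.1, restate the power or SD ceiling from the 7.2 model at the split the allocation list will produce: for example, an SD of at most about 214 pg/ml for 85% power at 8:7, or about 190 at 11:4.
3. In 6.2, state how the remaining subjects are allocated and which sequence a replacement receives, so that the figure can be checked.

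Weighting the remaining list toward placebo-first would recover most of the loss. That is an option for the statistician, not a required change.

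The cost is protocol wording and one recalculation, with no extra participants and no change to the list. The drawback is a somewhat less favourable stated power or ceiling.

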6.4 Clinical Procedures

6.4.1 Treatment Regimen

This study will consist of two 2-day intervention visits separated by approximately 8 weeks.

Subjects will be asked to report to the research center by 7 am on the first day of the study after fasting overnight. On arrival, intravenous lines will be placed in each arm (one will be used for infusions and the other for blood sampling). A minimum of 30 minutes after the IVs are placed, baseline blood samples will be drawn for later measurement of glucose, glucagon, epinephrine, norepinephrine, and cortisol. Subjects will then be given a 4 mg (0.1 ml) or 8 mg dose (0.2 mL of IN naloxone or a similar volume of IN placebo.. After naloxone or placebo dose, a hyperinsulinemic (2.0 mu/kg/min) hypoglycemic (target = 50 mg/dl) clamp protocol will be started. The clamp will be maintained for 2 hours. Blood samples will be collected every 5 minutes for monitoring of blood glucose levels and every 15 minutes during the last 90 minutes for later measurement of serum glucagon, epinephrine, norepinephrine and cortisol. If the subject received 4mg dose of IN naloxone or placebo, a second dose of 4 mg IN naloxone or placebo will be given at +30 min after the start of insulin clamp. Every 15 minutes during the last 90 minutes minutes of the morning clamp, subjects will be asked to quantitate their hypoglycemia related symptoms using a standardized questionnaire (12). At the completion of the morning clamp, glucose will be given to return the participant to normal glucose. 2 hours after the end of the morning clamp, a second 2 hour hyperinsulinemic (2.0 mu/kg/min) hypoglycemic (target = 50 mg/dl) clamp protocol will be started. At the start of this afternoon clamp study, a dose of 4 mg or 8 mg of IN naloxone or placebo will be given. Afternoon clamp will proceed as in the morning except that no serum or plasma will be collected except for the monitoring of glucose and collection of samples for subsequent measurement of naloxone. If the subject received 4 mg dose of intra-nasal naloxone or placebo, a second dose of 4 mg intra-nasal naloxone or placebo will be given after 30 minutes. After the completion of the afternoon clamp, subjects will be returned to euglycemia and fed a meal. They will then be allowed to leave the research center with instructions to return the next morning after an overnight fast. At 7 AM on day 2 they will undergo a single 2 hour hyperinsulinemic hypoglycemic clamp (target blood glucose 50 mg/dl) during which blood samples will be collected as on the morning of day 1. Symptom scores will be collected every 15 minutes during the last 90 minutes of the clamp. At the end of the study, infusions will be stopped, and participants will be fed a meal and then sent home after they are scheduled to return for Part 2 in 8 weeks. This timing is selected to ensure that female participants are studied at the same phase of the menstrual cycle; males will return for Part 2 in 8 ± 2 weeks. During Part 2 they will receive the treatment not provided during Part 1. The rest of the study protocol will be the same as in Part 1.

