6.4.2 Clinical Assessments During Study

Blood Pressure & Pulse: A CRU staff member will check and record blood pressure and pulse prior to, and then approximately 30 minutes following, each dose and prior to discharge.

Other Side Effects/Tolerability: Side effects and tolerability of the IN administration will be collected as self-reports by subjects during both part 1 and part 2.

Assessment of Safety: Safety assessments include adverse events during the 6-hour period of observation.

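### Over-labeling is the only protection for the participant blind, so participants who receive both devices may infer which Part was naloxone

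*Combined protocol and SAP*

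**What the plan says.** Section 5.1 states: "This is a single center, single-blind randomized cross over design trial". It explains that double-blinding was ruled out because "we will not be able to replicate for the placebo (placebo) the same delivery device"; the reason given is that "the manufacturer is unable to provide placebo-charged devices for us to use as placebo". For the participant's blind it offers one measure: "Our own labeling will be put over both naloxone and placebo devices in order to obscure any device labeling".

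The other sections that touch on the products add no masking of appearance:

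- Section 3.1 describes the placebo as a saline nasal spray.
- Section 3.2.1 has the two products coming from different suppliers.
- Section 3.2.2 has the investigators prepare the doses and give them on site.
- Section 6.2 covers only who prepares and who implements the randomization order.
- Section 6.4.1 matches the placebo to naloxone on approximate volume. It also has each participant cross to the other product in Part 2, about 8 weeks later.

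Two sets of outcomes depend on what the participant reports. Section 6.4.1 collects hypoglycemia symptom scores every 15 minutes in the last 90 minutes of the morning clamps on both days. Section 6.4.2 says: "Side effects and tolerability of the IN administration will be collected as self-reports by subjects during both part 1 and part 2".

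**The concern.** If the devices differ in shape, feel or action, a label over the print leaves that difference in place. In a parallel-group trial a participant would meet one device and have nothing to compare it with. In this crossover each completer meets both, so the comparison is made within the person, as the treatment contrast is.

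A participant who has worked out which Part was naloxone may score symptoms or report side effects in line with what they expect. Both matter to the trial's purpose. Better recognition of hypoglycemia symptoms is part of the long-term hypothesis in section 2.0, and tolerability is one of the reasons section 5.1 gives for treating up to 8 participants with naloxone first. With no treatment guess recorded, a reader of the results could not tell whether the blind had held.

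**Working it through.** The plan attaches no figure to the blind, so there is none to reproduce. The check is whether the text supports a route from over-labeling to unblinding, and which outcomes such a route would reach.

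**1. Can the device be a cue?** Section 5.1 says the same device cannot be used for both products. Over-labeling hides print only. I found no screen, sleeve, eye cover or common applicator in 3.2.1, 3.2.2, 5.1, 6.2, 6.4.1 or 6.4.2. So any difference in the devices remains open to the participant.

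**2. Is the device enough by itself?** No. A different device in Part 2 shows that the product changed, which a participant who knows the design already expects. A second cue is needed to say which product was which.

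**3. Do the documents supply a second cue?** Yes. Section 2.0 lists dryness, swelling, congestion and inflammation of the nose after a single 8 mg naloxone dose, and the risk table in 8.4.1 repeats them. The same table reports no adverse events for nasal placebo. It also plans a standardized form that asks about these effects by name.

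**4. How often is the participant exposed?** Section 3.2.2 gives four or two administrations per Part, depending on the regimen. The visit table in 6.4.1 shows three for the 4 mg regimen. Those passages need reconciling, but this point holds with any of the counts.

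**5. What would reach the epinephrine contrast?** Let τ be the true treatment effect and π the period effect (Part 2 minus Part 1). The mean Part 2 minus Part 1 difference is π − τ with naloxone first and π + τ with placebo first. The period-adjusted estimate is half the difference between the sequences: [(π + τ) − (π − τ)]/2 = τ. Now add an expectation shift in Part 2, assuming participants guess correctly:

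| Shift in Part 2 | Estimate | Bias |
|---|---|---|
| s in everyone | [(π + s + τ) − (π + s − τ)]/2 | 0 |
| e only in those who believe they have naloxone | [(π + τ + e) − (π − τ)]/2 | e/2 |
| +e under naloxone, −e under placebo | [(π + τ + e) − (π − τ − e)]/2 | e |

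Only a shift that differs by treatment gets through, and the share that does depends on its pattern. Under the section 5.3.1 endpoint (the difference between Day 1 and Day 2 peaks), a shift common to both mornings of a Part cancels earlier still. Under the section 7.2 outcome (the peak in the third clamp) it does not. The documents give no value for e, so no bias can be computed.

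**6. Which outcomes are exposed?** The same algebra holds for the self-reported scores, where an expectation effect is far easier to credit than on a plasma hormone. Naloxone pharmacokinetics, the secondary endpoint in 5.3.2, are not plausibly open to expectation.

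**The case against.** The strongest reply is that the protocol is candid about a supply constraint, and that this is a small Phase 1 proof-of-principle study with a laboratory endpoint. Epinephrine is measured in plasma sent to an outside core laboratory (6.3.3). No spray is given on Day 2, when the third clamp is measured. Symptom scores are neither a primary nor a secondary endpoint, and section 7.2 plans no analysis of them. The two sets of exposures lie about 8 weeks apart, and people with a history of narcotic abuse, who might know the commercial product, are excluded (5.4.6). All of this stands. It limits the point to the self-reported outcomes and to the strength of the single-blind claim.

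Several stronger readings are tempting, and the documents do not support them:

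- A reader might infer that participants handle the devices. Section 3.2.2 has the investigators prepare and give the doses, and self-administration is not stated.
- A reader might infer that the devices look plainly different. Section 5.1 says only that the same device cannot be used, and neither device is described.
- A reader might infer that a changed device reveals the treatment. It confirms a switch that the design already implies; a further cue, such as the nasal effects, is needed.
- A reader might infer that any expectation effect on epinephrine passes in full into the treatment contrast, or that the epinephrine result could no longer be read as a drug effect. The table above shows that the share can be none, half or all, and nothing in the documents shows that anticipation moves epinephrine materially during clamped hypoglycemia.

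**Conclusion.** The point holds as a risk to the participant blind, not as a demonstrated failure of it. The single-blind claim rests on over-labeling alone, every completer receives both products, and the listed nasal effects give participants a way to tell the two Parts apart. The exposed outcomes are chiefly the symptom scores and the side-effect and tolerability reports. For epinephrine an effect is possible but unsized.

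The conclusion rests on two assumptions: that participants see or feel the device when the spray is given, and that the nasal effects listed for naloxone occur often enough here to be noticed. The documents settle neither. I class this as a cheap improvement.

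**What to change.** 1. In sections 5.1 and 6.4.1, require that study staff give every spray in both Parts with the device out of the participant's sight. The eyes can be covered briefly, or an identical opaque cover used if one fits both devices; the documents do not show whether one would.
2. At the end of Day 2 of each Part, after all outcomes are collected, ask which treatment the participant believes they received. Report the guesses by treatment and Part. Read them as descriptive: a correct guess may come from the device, the nasal effects or a real benefit.
3. In the study summary and section 5.1, describe the participant blind as partial, because step 1 cannot hide the feel of actuation or the nasal effects. Interpret symptom scores and tolerability with that in mind.

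The cost is a minor step at each dosing and one CRF question per Part. Asking at the end of Part 1 may draw some attention to the question before Part 2, which is a small price for knowing whether the blind held. No dose, visit or blood sample changes.
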